4.2 Enrollment of patients receiving facility-based care and not engaged in microfinance ³

Among AMPATH patients not participating in group microfinance, the Aim 1 enrollment period will begin on August 1, 2021 and end when the enrollment target of n=300 standard care patients has been met. Obtainment of written informed consent will be recorded in REDCap. The following steps specify the process that will be used for matching and enrolling 300 standard of care patients.

Step 1. Using AMPATH's Medical Record Systems (AMRS), the project's data manager will filter all patient records in AMRS so that only those SOC patients who meet the following eligibility criteria are selected:

- Age: 18 years of age or older
- County of residence: Busia or Trans Nzoia
- County where patient receives care: Busia or Trans Nzoia
- HIV Status: currently living with HIV
- ART Status: Has been taking ART medications for ≥ 6 months
- Pregnancy Status: Not currently pregnant at most recent HIV care visit
- CARG Status: Not a member of a community ART group (CARG)

Filtering all AMRS patients by eligibility criteria will create a master list (**List 1**) of AMRS patients who can be matched to enrolled microfinance group members. List 1 will need to contain at least 1200 patients (300 SOC patients with 4 potential backups).

Step 2. Each time a group of GISHE participants are newly enrolled in Study Arm A or B (e.g., monthly or quarterly), the study's Data Assistant will send a list of the newly enrolled GISHE group members to the Data Manager so that the Data Manager can match these GISHE participants 3:1 to eligible SOC patients from List 1. The list of newly enrolled GISHE group members will contain, at minimum, the following information:

- Harambee Study ID
- AMRS ID (if available)
- CCC Number (if available)
- Universal ID (if available)
- County of Residence (Busia or Trans Nzoia)
- Age
- Gender

³ See the Addendum to the overall project protocol starting on page 100 for changes made to the standard of care matching process.

• Name of health facility where patient receives routine HIV care

The Data Manager should match SOC patients from List 1 to enrolled GISHE group members on:

- (1) County of Residence,
- (2) Age (within +/- 5 years of the GISHE participant's age),
- (3) Gender, and
- (4) Health Facility

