- The study assessments will be conducted at community locations that are convenient for participants
- We will hire appropriately-trained staff members to conduct recruitment and retention activities; many staff members have already been working with the MF groups for a number of years

Participant retention in the SOC arm: Research personnel will attempt to contact identified eligible SOC participant up to 2 times to invite them to enroll in Aim 1. Research personnel will attempt to contact each enrolled SOC participant up to two times to complete the 18-month follow up assessment (i.e., viral load and surveys). In the event that a participant cannot be located, their most recent viral load measurement will be ascertained from the patient's AMRS data to estimate viral suppression at 18 months.

5. Aim 1 RCT Methods: Randomization ⁴

Group randomization will occur after all consenting participants complete baseline assessments using a computer-generated sequence to randomize MF groups to receive either integrated community-based care (ICB) or standard of care. The randomization process will be conducted centrally by biostatisticians at Brown University.

6. Aim 1 RCT Methods: Intervention Delivery ⁵

Integrated care visits will occur monthly during months 1-6 of the trial, and then quarterly for the remaining months (7-18). Initial intervention group visits (months 1-6) will focus on acute non-HIV related needs and screening for NCDs, such as diabetes and hypertension. Facilities will be informed that participants will be receiving HIV care outside of clinic for the duration of the study, unless additional care is required (i.e., referral to facilities for worsening HIV, acute care, hospitalization, etc.). Protocols

⁴ See the Addendum to the overall project protocol starting on page 100 for changes made to the randomization process.

⁵ See the Addendum to the overall project protocol starting on page 100 for changes made to the schedule and format of intervention delivery.

for handling new opportunistic infections, suspected viral resistance, malignancy screening and diagnosis will follow established AMPATH care protocols.

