11. What concerns do you think patients may have about integrating HIV care into microfinance groups?

Probes:

- What do you think they may like about this integrated care model?
- What do you think they may dislike about this integrated care model?

Additional comments

12. Is there anything else that is important for me to understand about community-based care delivery from your perspective? How about microfinance groups? How about the integration of HIV care into microfinance groups?

Closing: Thank participant for their time. Remind participant about the confidentiality of the interview. Ask if they have any questions about anything that was discussed.

EXAMPLE: Thank you for your time and for sharing your thoughts with us. We want to remind you that your comments will remain confidential. Do you have additional questions or comments?

Appendix VIII: NCD screening protocol at study baseline (implemented in all microfinance groups (Study Arms A and B)) **Hypertension (HTN)** Diabetes (DM) Screening Screen for HTN in community groups¹ Screen for DM in community groups (study baseline) FBS < 6.0 mmol/L and FBS \geq 6.1 mmol/L or SBP < 140mmHg SBP ≥ 140mmHg or RBS \leq 7.7 mmol/L RBS \geq 7.8 m/mol/L and DBP < 90mmHg DBP > 90mmHg Perform HbA1C NOW test Discharge Patient needs confirmatory screening in 1 month HbA1C < 6.5 mmol/mol HbA1C ≥ 6.5mmol/mol Counsel on primary prevention; Patient has confirmed DM. begin or continue treatment Discharge Screening (confirmatory 1-month confirmatory screening not required Confirmatory screening for HTN in community group after 1 month) SBP > 140mmHg or SBP < 140mmHg and DBP < 90mmHg DBP > 90mmHg Discharge Patient has confirmed HTN; begin or continue treatment

SBP: systolic blood pressure; DBP: diastolic blood pressure; FBS: fasting blood sugar; RBS: random blood sugar; HbA1C: hemoglobin A1C. Screening for hypertension and diabetes was conducted in the community for all microfinance group members randomized to standard, facilitybased (usual) care and to microfinance group members randomized to the integrated, community-based care intervention.

Addendum to the overall project protocol

This addendum summarizes changes that were made to the overall project protocol after the start of Aim 1 data collection on November 25, 2020.

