- 1. The eligibility criteria in the original project protocol required that a group had to be an active, AMPATH-affiliated Group Integrated Savings for Health Empowerment (GISHE) group in order to enroll in the study. This criterion was revised during the recruitment period such that any active, community-based microfinance group (GISHE and non-GISHE) were eligible to enroll in the trial as long as a majority of their members received HIV-related care at an AMPATH facility. This change was made to maximize sample size given that many GISHE groups had transitioned to community ART groups at the time of study recruitment.
- 2. The original protocol stated that, among microfinance groups randomized to the intervention arm, integrated community-based care visits would occur monthly during months 1-6 of the trial and then quarterly for the remaining months (i.e., months 7-18 of the trial).

Starting in October of 2021, integrated care visits were no longer delivered monthly during months 1-6 of the trial, and instead were delivered less frequently during months 1-6. Specifically, microfinance group enrollment and follow-up occurred in four phases, such that:

- Phase I intervention groups in Busia and Trans Nzoia County received monthly visits during months 1-6 of the trial, and quarterly visits thereafter (in accordance with the original protocol).
- Phase II intervention groups in Trans Nzoia County received monthly visits during months 1-6 of the trial, and quarterly visits thereafter.
- Phase II, Phase III and Phase IV intervention groups in Busia County received monthly visits during the first three study visits (i.e., months 0 2 of the trial), and quarterly visits thereafter (i.e., from months 3 18).

This change to the intervention delivery schedule was made to reduce administrative burden on clinical officers and study staff traveling to remote community meeting locations. Quarterly (rather than monthly) visits were still in keeping with AMPATH care protocols which most commonly recommend quarterly ART distribution for clinically stable HIV patients.

3. The original project protocol stated that integrated community-based care would be delivered to intervention groups at monthly microfinance group meetings by a clinical team comprised of the same cadre of workers who deliver care in AMPATH-supported facilities (clinical officer, pharmacy technician, peer navigator, social worker).

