The protocol was revised after the start of enrollment (in November 2020) and prior to the start of the first integrated care visit in the community (in May 2021) such that solely a clinical officer attended each integrated care visit. This change was made to minimize the amount of attention drawn to intervention recipients during study visits in the community (e.g., to help minimize the potential for HIV-related stigma), to have community-care visits more closely mimic the personnel present during facility-based HIV visits, and to minimize administrative costs. The change was also made based on recommendations from AMPATH leadership and Ministry of Health personnel working in the respective study counties; these personnel suggested having minimal care personnel travel to the community as a way to minimize administrative costs and increase the likelihood the established HIV care and CDM programs would be able to take over the intervention model after study completion.

The clinical officer who delivered community-based care worked closely with facility-based personnel, including a pharmaceutical technician (helped with packaging of drugs), retention worker (assisted with tracking down lost-to-care participants), other facility-based clinical officers (received participants who were referred back to facility for emergencies, released participants who were eligible for community-based care), health records officers (facilitated access to patients records for data entry and/or retrieval as needed). For all microfinance groups, a phlebotomist attended the 18-month study visit in the community to collect blood samples to assess the study's primary outcome.

- 4. The original project protocol assumed that attending routinely scheduled microfinance group meetings would serve as a sufficient, built-in incentive for remaining engaged in the study and attending study visits. However, the study received Moi University Institutional Research and Ethics Committee (IREC) approval on April 20, 2021 to provide an inconvenience fee of 300 KES (~\$2.5) for each survey assessment that enrolled study participants completed during the randomized trial. The study received IREC approval on April 20, 2021 to provide an inconvenience fee of 300 KES as well as lunch/refreshments to study participants and key stakeholders who participated in the Aim 2 in-depth interviews. The provision of inconvenience fees aimed to maximize retention and increase equity in human subjects research.

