and capital (e.g., fuel) resources needed to travel to the distinct health facilities to ascertain secondary outcome data for each matched patient were prohibitively high.

- 8. In order to enroll 300 patients receiving standard facility-based care and not engaged in a microfinance group (SOC), the original protocol stated that enrolled microfinance group participants should be matched 3:1 to eligible SOC patients on county, gender, age (+/- 5 years), and health facility. The matching protocol was revised on February 8, 2022 such enrolled microfinance group participants were matched 3:1 to eligible SOC patients on gender and age (+/- 5 years of microfinance participant). This change was made because most SOC patients who were invited to enroll in Busia County after February 8, 2022 were ineligible for study participation due to membership in either a microfinance group or a community ART Group. This change resulted in approximately 90 enrolled microfinance group members in Busia County being matched to 30 SOC patients in Trans Nzoia County on (1) age (within +/- 5 years of the GISHE participant's age) and (2) gender.
- 9. The original project protocol stated that group randomization would occur using a computer-generated sequence to randomize microfinance groups to receive either integrated community-based care (ICB) or standard of care, and that the randomization process would be conducted centrally by biostatisticians at Brown University.

The cluster randomization approach was revised to use a transparent, community-engaged approach to increase transparency and cultivate trust between research personnel and study participants, clinical personnel, and local community leaders. Below is a summary of the steps that were implemented for at each community-engaged randomization ceremony. Six randomization ceremonies were conducted among the 57 microfinance groups following enrollment:

- 2 randomization ceremonies each with 10 microfinance groups were conducted in Phase I groups
- 2 randomization ceremonies each with 11 and 8 microfinance groups were conducted in Phase II groups
- 1 randomization ceremony with 15 microfinance groups was conducted in Phase III groups
- 1 randomization ceremony with 3 microfinance groups was conducted in Phase IV groups

The below steps describe the community-engaged randomization process.

Participants

- 1. Group leaders (Chairperson, Secretary & Treasurer)
- 2. AMPATHPlus Senior Technical Officers (STO)

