- 7. In each county, 10 group leaders from each of the 10 GISHE groups took turns selecting a raffle ticket.
- 8. The group leads then held onto their tickets until all the leads had picked their ticket.
- 9. Once all the leads had a ticket, the leads opened their tickets together and show them to the community attendees.
- 10. The raffle tickets were randomized into the respective Study Arms based on the label as aforementioned in 6a
- 11. Group leads were congratulated and given a chance to ask questions/seek any clarifications

Post Randomization

- 1. Project Manager communicated the randomization outcomes to the larger research team.
- 2. Group representative (group leads) present during the randomization communicated the randomization outcomes to their respective groups.
- 3. Align the Return to Care (RTC) dates for all the Study Arm A members.

10. The original Aim 1 analysis plan for the primary outcome (virologic suppression) that is summarized in section 7.2 of this protocol and in the published protocol ([name] BL et al. Integrated community-based HIV and non-communicable disease care within microfinance groups in Kenya: study protocol for the Harambee cluster randomised trial. BMJ Open. 2021 May 18;11(5):e042662. doi: 10.1136/bmjopen-2020-042662.) was revised. Details of the revised analysis plan, and reasons for the revision(s), are described in the following paragraphs.

Revised Analysis plan

Primary objective: Compare rates of viral suppression between the MF+ICB and MF+UC arms.

Secondary objective 1: Compare rates of viral suppression between the MF+ICB and UC arms.

Secondary objective 2: Compare rates of viral suppression between the MF+UC and UC arms.

Primary outcome definition: Achievement of HIV-1 RNA viral load suppression at 18-months. Participants whose 18-month viral load assessment occurred before January 1, 2023 were considered virologically suppressed if their viral load was <400 copies/mL. To adhere to changes to Kenya's national recommendations for HIV monitoring cutoffs that occurred during the trial, patients whose 18-month viral load assessment was on or after January 1, 2023 were considered suppressed if their viral load was <200 copies/mL.

Analysis set: The analysis set for all objectives is the intent-to-treat set and included all randomized participants for arms MF+ICB and MF+UC and all participants that in the UC arm that provided informed consent.

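### By planned dates the calendar cutoff scores Arm C at <200 copies/mL and early microfinance participants at <400, and an Arm C-only carry-forward rule is unreconciled; both bear on comparisons with Arm C, not materially on A vs B

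*Combined protocol and SAP*

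**What the plan says.** **Cutoff.** Addendum items 5 and 10 apply one calendar rule to every participant: <400 copies/mL if the 18-month assessment fell before January 1, 2023, and from then on "patients whose 18-month viral load assessment was on or after January 1, 2023 were considered suppressed if their viral load was <200 copies/mL".

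**Dates.** Section 4.2 states: "Among AMPATH patients not participating in group microfinance, the Aim 1 enrollment period will begin on August 1, 2021". Item 8 revises the Arm C matching as of February 8, 2022, because of ineligibility among "most SOC patients who were invited to enroll in Busia County after February 8, 2022"; about 30 Arm C patients were matched across counties as a result. For the microfinance arms, section 4.1 plans enrolment from November 1, 2020. The addendum opens by describing changes made "after the start of Aim 1 data collection on November 25, 2020", and item 3 places a change "prior to the start of the first integrated care visit in the community (in May 2021".

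**Analysis of the Arm C contrasts.** Item 10 uses a doubly robust GEE with a model for dropout and assumes that dropout is non-informative. Its rationale reports a rerun with <200 for all participants and says the results were very similar to the primary analysis. It gives no estimates and does not name the contrasts covered.

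**Record values.** Section 4.3, on retention in the SOC arm, says: "In the event that a participant cannot be located, their most recent viral load measurement will be ascertained", taken from AMRS to stand for suppression at 18 months. It sets no limit on the age of the result. Section 7.1.2 offers microfinance members who miss an assessment a rescheduled meeting and states no carry-forward. Item 6 allows a record result for any participant if it dates from the 3 months before the 18-month assessment. Section 6.2, written for the integrated care arm, keeps mid-trial results out of the effectiveness analyses. No addendum item withdraws the section 4.3 rule.

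**The concern.** A calendar cutoff is neutral between arms only when the arms are assessed over the same calendar period. Arms A and B were randomized together in ceremonies, so they share it closely. Arm C is not randomized and was planned to open about nine months after microfinance enrolment. A value of 200-399 copies/mL then counts as success in an early microfinance participant and as failure in an Arm C participant, so the direction is known: towards A and B.

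The carry-forward rule raises a related problem. Read literally, the same event (a participant who cannot be found) gives an observed outcome in Arm C and a dropout in Arms A and B. With routine testing every 12 months (section 6.2), the carried value could be many months old.

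At stake are secondary objectives 1 and 2 (A vs C and B vs C), which test part of the A>B>C working hypothesis, and Aim 3, where section 9.2 defines incremental effectiveness against SOC.

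**Working it through.** **1. Which cutoff applies, by nominal date (start + 18 months).**
- Arm C opening: August 1, 2021 gives February 1, 2023, 31 days after the cut-over: <200.
- Arm C after the matching revision: February 8, 2022 gives August 8, 2023: <200.
- Start of Aim 1 data collection: November 25, 2020 gives May 25, 2022: <400.
- First integrated care visit: May 2021 gives November 2022: <400.
- Dividing line: a baseline of July 1, 2021 gives January 1, 2023.

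**2. If the test date governs instead of the visit date.** With the 3-month window, the dividing line moves to October 1, 2021 (+18 months = April 1, 2023; −3 months = January 1, 2023). Arm C participants enrolled in August or September 2021 who have a qualifying record result could then fall under <400, which shrinks the artefact from the Arm C side. The same reading could also move some microfinance participants with baselines in July to September 2021 to <400. The documents do not say which date governs and give no counts.

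**3. Share of A/B assessed before 2023.** The ceremonies in item 9 sum to 10 + 10 + 11 + 8 + 15 + 3 = 57 groups, matching the stated total. The phases are not dated, so the share is an assumption, and groups stand in for participants as if of equal size. The working case is all of Phase I: 20/57 = 35.1%. A low case is 10/57 = 17.5%. An upper bound adds all of Phase II ("2 randomization ceremonies each with 11 and 8 microfinance groups were conducted in Phase II groups"): 39/57 = 68.4%.

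**4. Size of the artefact.** Artefact = (share of A/B before 2023) × (share at 200-399 copies/mL). The second factor is not in the documents; 0.5-3% is assumed.
- 35.1%: 0.18 to 1.05 points
- 17.5%: 0.09 to 0.53 points
- 68.4%: 0.34 to 2.05 points

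**5. Against the precision of A vs C.** Assume 90% suppression, a mean cluster of 900/57 = 15.8, the plan's ICC of 0.05 and 15% dropout, and no clustering in Arm C.
- Design effect = 1 + (15.8 − 1) × 0.05 = 1.74
- SE = sqrt(0.09 × (1.74/382.5 + 1/255)) = 2.76 points (2.79 with the plan's group-size SD of 5)
- At the 35% share: 0.175/2.76 = 0.06 SE to 1.05/2.76 = 0.38 SE
- With no true effect, a two-sided 5% test then rejects 5.05% to 6.7% of the time.
- Odds ratio from the artefact alone, odds(0.90 + artefact)/odds(0.90): 1.02 to 1.13. At 95% suppression it is 1.04 to 1.28.

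**6. A vs B.** Item 9 splits each ten-group ceremony 5/5, so Phase I is 10 and 10. If the other ceremonies split as evenly as they can, the arms have 27 to 30 groups. The largest difference in early share is 10/27 − 10/30 = 3.7 points; × 3% this is 0.11 points.

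**7. Carry-forward.** No calculation is possible: neither the number of Arm C participants scored this way nor the age of their results is given.

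**The case against.** The strongest reply is that the cutoff question has been answered: the <200-for-all rerun is reported after the secondary-objectives plan, and the analysis set for all objectives includes Arm C, so it may cover these contrasts. That is a fair reading, but the sentence compares with the primary analysis. Similar results for A vs B would be expected in any case, because that contrast is nearly balanced on date.

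Second, August 1, 2021 is a planned date and the rule uses actual assessment dates. This stands: a reader might infer that all of Arm C was in fact scored at <200, and the documents do not show that.

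Third, the effect is small against the planned 15-point difference, in contrasts that already rest on no unmeasured confounding. This also stands. The upper-bound case (2.05 points, 0.74 SE, 11.5% rejection) should not be read as likely. It needs every Phase II group to have started before July 2021, yet Phase II groups in Busia followed the reduced schedule: "Starting in October of 2021, integrated care visits were no longer delivered monthly during months 1-6 of the trial".

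Fourth, a reader might blame the models for omitting assessment date. That is not the defect. By nominal dates Arm C has no assessments before 2023, so there is no overlap to adjust on, and adjustment cannot repair a difference in scoring.

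Fifth, the dropout model in item 10 is later and more specific than section 4.3, which is consistent with the carry-forward never having been used. It does not establish that, so bias from carry-forward cannot be inferred either.

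**Conclusion.** The point holds in limited form. By nominal planned dates, the calendar rule scores Arm C and early microfinance participants at different cutoffs, in a direction that can favour A and B in A vs C, B vs C and Aim 3 effectiveness against SOC. At an assumed 35% early share and 0.5-3% at 200-399 copies/mL, the artefact is about 0.2 to 1.05 points (0.06 to 0.38 SE at 90% suppression), which is minor. It could be smaller if the test date governs for Arm C, and it disappears under <200 for all if that rerun covers these contrasts.

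The Arm C carry-forward is a separate, unresolved conflict between section 4.3, the 3-month window in item 6 and the dropout model in item 10. Its use and effect are unknown.

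A reader might infer that the primary result is compromised. The documents do not support this: the date rule is nearly balanced between A and B, and the carry-forward is stated for Arm C alone. Confidence is medium, because actual assessment dates and the distribution of viral loads are not given.

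**What to change.** 1. **Cutoff.** Run and report <200-for-all estimates, with confidence intervals, for A vs C and B vs C as a named analysis beside the date-dependent definition. Base the interpretation of these contrasts on whether the two agree. If the existing rerun covered them, report it. State whether the test date or the visit date sets the cutoff. The A-vs-B definition need not change.
2. **Ascertainment.** For the Arm C contrasts, use one rule in all arms: the 18-month draw, or a record result from the prior 3 months, with everyone else treated as a dropout in the existing doubly robust GEE. Use older carried-forward Arm C values only in a sensitivity analysis, and report their number and age. State whether the section 4.3 rule was applied.

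The work is recoding viral loads already held and rerunning existing code. There are three costs. Arm C gains some missing outcomes (number unknown). The analysis leans on non-informative dropout for unlocated patients, where that assumption is least secure; the sensitivity analysis shows how much this matters. And it would be specified after results were known, so it should be labelled as such. Keeping the date-dependent definition alongside avoids replacing, after the fact, one that the plan says was set without looking at the data.

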4.1 Enrollment of microfinance group members

After identifying eligible microfinance group members, project personnel will use Adult Consent Form I (Appendix I) to obtain written informed consent from eligible GISHE group members (who will later be randomized to Study Arm A or to Study Arm B). For eligible GISHE group participants, informed consent will be collected in-person during a regularly scheduled GISHE group meeting.

Among microfinance group members, the Aim 1 enrollment period will begin on November 1, 2020 and end when the enrollment target of n=900 GISHE group members has been met. Obtainment of written informed consent will be recorded in REDCap.

General Steps for Obtaining Written Informed Consent

- The informed consent process should always occur in a private, confidential, and safe location.
- Elaborate on the objectives and purposes of the study and why the potential participant may qualify. Review the procedures that will be required of the participant. This includes naming the procedures, the time duration of the study, and location of where it will take place. Describe all of the risks and benefits for the procedures that are involved. Ensure that the potential participant has sufficient time to ask questions.
- If the subject is willing to participate under his or her own free will or the subject's legally authorized representative (LAR) agrees to the subject's participation, informed consent should be documented in the following ways:

- a. The subject or the subject's legal representative signs, personally dates and prints his or her name in block letters on the consent form; and
- b. The person who conducts the informed consent process signs, personally dates and prints his or her name in block letters on the consent form.
- Provide a paper copy of the signed and dated ICF to the subject and/or the subject's LAR.
- Store all signed informed consent forms securely in compliance with local IRB approvals and following the study's Aim 1 Data Management Protocol.

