Stability analysis: We performed stability analysis to determine how sensitive the results were to different specifications of the model used in the implementation of the doubly robust generalized estimating equation. This was done by modeling continuous covariates using second order polynomials and including interactions between the covariates. The results were similar to what is presented in the main manuscript.

Analysis plan for secondary objectives: The analyses of both secondary objectives were conducted using a doubly robust generalized estimating equation with a logit link function accounting for potentially differential dropout and confounding⁸. The generalized estimating equation models included the intervention arm, used an independence working correlation matrix and the variance was estimated using a sandwich variance estimator for clustered data. The intervention effects were estimated using the log odds ratio coefficient of intervention in the generalized estimating equation. The primary hypothesis tests of the intervention effects were conducted using a Wald test and 95% Wald-based confidence intervals were calculated.

Handling of confounding and dropout: Implementation of the method relies on specifying a model for the dropout probability and two outcome models (one for each treatment arm) and these procedures account for both dropout and confounding (under the assumption of no unmeasured confounding and a non-informative dropout). All three models were logistic regression models with linear main effects of county, log(viral load at baseline+1)), schooling achieved, age, and gender and the model for dropout probability also included the treatment arm.

Handling of missing data: Multiple imputation was used to account for missing data on baseline covariates and Rubin's rule for variance estimation was used for variance estimation.

Rational for revisions to original analysis plan:

We modified the primary outcome definition without looking at the data and to be in compliance with national guidelines that changed during the study's follow-up period. As a sensitivity analysis we reran the analysis with the current definition of viral suppression (i.e., <200 copies/mL) used for all participants, and the results were very similar to what the primary analysis shows.

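### Arm C's planned enrolment opens nine months after the microfinance arms and no calendar-time term is used, so part of any secular change in suppression may be read as an effect in the two usual-care contrasts

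*Combined protocol and SAP*

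**What the plan says.** Section 4.1 states that, for microfinance members, "the Aim 1 enrollment period will begin on November 1, 2020". Section 4.2 states that, for patients outside microfinance, "the Aim 1 enrollment period will begin on August 1, 2021". The Addendum's opening paragraph puts the actual start of Aim 1 data collection at November 25, 2020, and Addendum item 3 puts the first community care visit in May 2021.

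Section 3.2 describes Arm C as a non-randomized matched comparison. Section 4.2 matches on county, age, gender and facility. Addendum item 8 reduces this to age and gender from February 8, 2022.

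Addendum item 10 analyses both secondary objectives (MF+ICB v UC and MF+UC v UC) with a doubly robust GEE that contains arm only. Of the dropout model and the two outcome models it says: "All three models were logistic regression models with linear main effects of county, log(viral load at baseline+1)), schooling achieved, age, and gender". The dropout model also contains arm. The analysis assumes no unmeasured confounding. The stability analysis it describes, given before the secondary objectives, uses second-order polynomials and interactions of the covariates. Enrolment date, phase and assessment date appear in none of these.

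**The concern.** In a non-randomized contrast, a variable that differs between the arms by design and may predict the outcome should be controlled or at least examined. Calendar time of enrolment is such a variable here. If suppression under ordinary care moved between late 2020 and 2023 for reasons unrelated to microfinance or community care, some of that movement enters MF+ICB v UC and MF+UC v UC.

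The documents give grounds to check. National monitoring cut-offs changed in August 2022 (Addendum item 5). Many GISHE groups had become community ART groups by the time of recruitment (item 1). Most Busia patients invited to Arm C after February 8, 2022 "were ineligible for study participation due to membership in either a microfinance group or a community ART Group" (item 8), so the pool from which Arm C could be drawn was restricted.

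At stake is the reading of two of the three arm comparisons. They carry the B>C and A>C parts of the working hypothesis in Section 3.4.

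**Working it through.** **Plan's own figure.** The plan gives no figure for calendar drift. Its one figure for these contrasts, power above 80% for a 15-point difference (Section 3.4.2), reproduces: 0.89 or more for both comparisons with Arm C after 15% dropout. It says nothing about bias.

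**Dates.**
- November 1, 2020 to August 1, 2021 is 273 days, nine calendar months.
- From the actual start of data collection (November 25, 2020) the gap is 8.2 months.
- From the first community visit (May 2021) it is 2 to 3 months.
- If Arm C opened as planned, its first patient reaches month 18 on February 1, 2023.
- Section 5 randomizes groups after baseline assessment, so groups visited in May 2021 had enrolled before Arm C's planned opening.
- Addendum item 9 lists 20 of 57 groups in Phase I (35%) and 37 of 57 (65%) in Phases II to IV.

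**Direction.** With no true effect and drift d in points per year, the expected contrast (microfinance minus UC) is −d × lag/12, because Arm C is measured later. Rising suppression (d > 0) pushes the contrast down; falling suppression pushes it up.

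**Size, under assumptions.** The documents give no trend and no enrolment dates by arm. Assumed: drift of 1 to 3 points a year; mean lag of 3 to 9 months; suppression of 90 to 95% (Addendum item 10 says only that it was high); no absorption by baseline viral load. From Sections 3.4.1 and 3.4.2: 450 per microfinance arm in 20 groups (22.5 each), 300 in Arm C, 15% dropout, ICC 0.05.

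- Analysed: 450 × 0.85 = 382.5 and 300 × 0.85 = 255.
- Design effect: 1 + 21.5 × 0.05 = 2.075 (Arm C unclustered).
- SE = √[p(1−p)(2.075/382.5 + 1/255)] = 2.90 points at p = 0.90 and 2.11 points at p = 0.95.
- Two-sided error = Φ(−1.96 + b/SE) + Φ(−1.96 − b/SE), where b = d × lag/12 in absolute value.

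| Drift (points/year) | Lag (months) | b (points) | Error, p = 0.90 | Error, p = 0.95 |
|---|---|---|---|---|
| 1 | 3 | 0.25 | 5.1% | 5.2% |
| 1 | 6 | 0.50 | 5.3% | 5.7% |
| 1 | 9 | 0.75 | 5.8% | 6.5% |
| 2 | 3 | 0.50 | 5.3% | 5.7% |
| 2 | 6 | 1.00 | 6.4% | 7.6% |
| 2 | 9 | 1.50 | 8.1% | 11.0% |
| 3 | 3 | 0.75 | 5.8% | 6.5% |
| 3 | 6 | 1.50 | 8.1% | 11.0% |
| 3 | 9 | 2.25 | 12.1% | 18.7% |

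Fourteen of the 18 cells are below 8.2%. A design effect of 1.95 (19.1 per group after dropout, SD of group size 5) changes the extreme cells only to 12.4% and 19.2%.

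**The case against.** **Lag.** A reader might take nine months as the typical lag. It is only the gap between planned openings. Microfinance enrolment ran in four phases (Addendum item 2), Section 4.2 matches Arm C in batches as groups enrol, and the Section 2 schedule places matching between pre-baseline and month 3. Phases II to IV may overlap closely with Arm C. Nor do the documents show that every Phase I group enrolled before the first Arm C patient; the May 2021 date establishes this only for the groups visited then. This objection stands.

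**All of a trend.** A reader might infer that any change over time is read in full as an effect. Only the trend multiplied by the imbalance in dates enters, and adjustment for baseline viral load may absorb part of a trend already present at entry. This stands in part. Under Section 6.2 the baseline value may be up to 12 months old and no test is done if none is on record, and item 10 imputes missing covariates. It cannot capture changes after enrolment.

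**Favouring microfinance.** A reader might suppose that improving care would flatter the intervention. With Arm C later, the opposite holds.

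**Evidence of a trend.** The recorded changes concern a monitoring cut-off and who could be recruited. Nothing in the documents shows suppression drifting. This stands, and it is why the size is unknown.

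**The rerun at <200 for everyone.** It deals with the cut-off alone, and item 10 compares it only with the primary analysis, without saying that it covered the Arm C contrasts.

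**Conclusion.** The point holds in a limited form. The two usual-care contrasts leave calendar time uncontrolled although the plan builds in a difference in enrolment dates. Part of a secular change may be read as an effect, with sign opposite to the trend. The table's range of about 5.1% to 19% rests wholly on assumed drift and lag. Its upper end needs both extremes together with 95% suppression and should not be quoted as an expected error rate.

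The randomized comparison of MF+ICB with MF+UC is not affected, because groups were allocated within phase-specific ceremonies (Addendum item 9). This is a cheap improvement to two secondary, non-randomized comparisons, not a defect in the primary result.

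**What to change.** As sensitivity analyses:

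1. Report enrolment dates and 18-month assessment dates by arm. The survey form records the interview date, and Section 6.2 already uses enrolment date to define baseline viral load.
2. Repeat both usual-care contrasts using only microfinance members enrolled from the date Arm C enrolment actually began.
3. Add enrolment date as one linear term to the dropout model and both outcome models, stating that estimates for the earliest phase rest on extrapolation, since the Arm C outcome model may have no patients at those dates.
4. Do the same for any retention comparison with Arm C. Addendum item 11 redefines that endpoint but gives no revised model.

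Quarter indicators are not advisable. With 255 Arm C outcomes and 90 to 95% suppression, only about 13 to 26 Arm C patients are unsuppressed (255 × 0.05 to 255 × 0.10), and item 10 already reports unstable fitting when monthly income was added to some models.

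The cost is one covariate, one restricted rerun, a wider interval and a smaller restricted sample.
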